reduced to a level the patient could tolerate, typically 50–60 L.min⁻¹. Patients were specifically instructed to breathe via their nose with a closed mouth and the percentage of time this was achieved was recorded (0%, 25%, 50% or 100%). After 3 min, the patients were asked to hold their breath for a few seconds while the HFNO was quickly removed and the nose clip re-attached. The patients then exhaled fully and continued to breathe for several breaths via the mouthpiece (delivering 21% oxygen) to ensure the highest value for EtO₂ was measured.

Patients in both groups then underwent a washout period for up to 5 min until the EtO₂ returned to within 10% of their baseline value. Once washout was completed, both groups repeated 30 s of tidal volume breathing followed by eight vital capacity breaths using their respective pre-oxygenation methods. During the initial 30 s of tidal volume breathing, the oxygen flow rate in the HFNO group was increased from 30 to 70 L.min⁻¹ and EtO₂ was measured at the conclusion of eight vital capacity breaths. The time taken to complete 30 s of tidal volume breathing and eight vital capacity breaths was also recorded.

Immediately after the study, patient satisfaction was assessed using a 5-category Likert scale for acceptability (acceptable, slightly acceptable, neutral, slightly unacceptable or unacceptable) and comfort (completely comfortable, slightly comfortable, neutral, slightly uncomfortable or completely uncomfortable).

Outcomes

The primary outcome was EtO₂ after pre-oxygenation, with factorial comparisons also being made between HFNO and standard flow rate facemask, and also between 3 min of tidal volume breathing and eight vital capacity breaths.

The Secondary outcomes were the proportion of patients achieving an EtO₂ ≥ 90%, percentage of time patients had their mouths closed during HFNO pre-oxygenation and tolerability (comfort and acceptability) of both pre-oxygenation techniques.

Sample Size Calculation

Study Protocol and Statistical Analysis

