The study sample size was determined based on a prior study demonstrating that the mean (SD) EtO₂ achieved following 3 min of pre-oxygenation in healthy, non-pregnant subjects with HFNO and facemask was 85.6% (6.4%) and 88.5% (6.2%), respectively. We initially powered the study for a non-inferiority comparison. The criterion for non-inferiority with respect to EtO₂ concentration achieved after 3 min was considered to have been met if the upper limit of a two-sided 95%CI for the absolute difference of EtO₂ concentration between groups was less than 10%. Using a non-inferiority design, assuming a non-inferiority margin of 10 and a standard deviation of 6.3, and that the HFNO group would have a mean approximately 3% lower than the control group, 26 patients (13 per group) were required to achieve a power of 90% with a type-1 error of 0.05. To account for attrition and study dropouts due to equipment errors (i.e. lack of a tight seal for waveform analysis), the sample size was increased to 40 (20 per group).

After patient recruitment we realised that as a physiological and not clinical study, a standard superiority design was more appropriate. Using a superiority analysis with 20 patients per group there would have been approximately 31% power to detect a difference in means of 3% with a standard deviation of 6.3.

Consequently, data for primary outcomes were analysed using mixed-effects linear regression. Mixed-effects models take into account the repeated-measures aspect of the data and control for correlations among measurements from the same patient. To determine if there was a difference in how the treatment groups responded, we tested for an interaction term between group and time-point. If a significant interaction was found, we followed it up with pairwise tests of the estimated marginal means between the groups at each time-point (e.g. HFNO baseline vs. control baseline) using the Kenward–Roger method to estimate confidence intervals, and controlling for multiple comparisons using Tukey's method. The proportion of patients achieving an EtO₂ ≥ 90%, comfort and acceptability was compared using Fisher's exact test. A p value < 0.05 was considered statistically significant. Statistical analysis was performed using RStudio version 1.0.153 (Integrated Development for R. RStudio, Inc., USA; <http://www.rstudio.com>) and R version 3.4.1, release date June 30, 2017 (The R Foundation for Statistical Computing, Austria).

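### Comfort and acceptability are ordered five-category outcomes, but Fisher's exact test ignores the order; for a directional shift at 20 per group this costs power, by an amount that depends on assumptions

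*Combined protocol and SAP*

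**What the plan says.** The patient-satisfaction paragraph, just before the Outcomes section, defines both scales. Acceptability is recorded on a "5-category Likert scale for acceptability (acceptable, slightly acceptable, neutral, slightly unacceptable or unacceptable" scale, and the parallel scale is "comfort (completely comfortable, slightly comfortable, neutral, slightly uncomfortable or completely uncomfortable". Both run from best to worst through a neutral midpoint.

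The Outcomes section lists "tolerability (comfort and acceptability) of both pre-oxygenation techniques" among the secondary outcomes.

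The last paragraph under Sample Size Calculation gives the analysis in one sentence, shared with the binary EtO₂ ≥ 90% outcome: "comfort and acceptability was compared using Fisher's exact test". The threshold is "A p value < 0.05 was considered statistically significant". No ordinal method, rule for collapsing categories, effect measure or power is given for the two scales. On size, "the sample size was increased to 40 (20 per group".

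**The concern.** The question behind a tolerability outcome is directional: do patients find high-flow nasal oxygen (HFNO) better or worse than the facemask? Fisher's test on a 2×5 table cannot use direction, because its p value is the same however the five columns are arranged. In a trial of 40 patients, a one-directional difference in comfort could be reported as not significant when a test that uses the order would have found it. A p value from a 2×5 table also tells the reader neither which group fared better nor by how much.

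**Working it through.** **1. The plan's own figure.** No power is stated for comfort or acceptability. The only superiority power given is about 31% for EtO₂ (difference 3, SD 6.3, 20 per group). Standardised difference: 3 / (6.3 × √(2/20)) = 3 / 1.992 = 1.506. Normal approximation: Φ(1.506 − 1.960) = Φ(−0.454) = 32.5%. The t-test calculation gives 31.2%, so the figure reproduces.

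**2. Does the test ignore order?** With column totals c_j and control counts a_j, the probability of a table is ∏ C(c_j, a_j) / C(40, 20). The p value sums this over all tables no more probable than the one observed. A product does not change when its factors are reordered, so neither does the p value.

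A hypothetical example (not trial data), best to worst category: control 10/5/3/1/1, HFNO 4/4/5/4/3.

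- Fisher: p = 0.24.
- Wilcoxon: column totals are 14, 9, 8, 5, 4, so the midranks are 7.5, 19, 27.5, 34, 38.5. Control rank sum = 75 + 95 + 82.5 + 34 + 38.5 = 325, against an expected 20 × 41/2 = 410. Tie-corrected variance = (400/12) × (41 − 4134/1560) = 1278.3, so SD = 35.75. With continuity correction, z = 84.5/35.75 = 2.36 and p = 0.018.
- With the categories rearranged (third, first, fifth, second, fourth), Fisher still gives 0.24 and Wilcoxon gives 0.51.

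**3. Size of the loss.** From the documents: five ordered categories, 20 per group, threshold 0.05 (taken as two-sided, since sidedness is not stated). Assumed, because the documents give nothing: the control distribution and the effect. Five control distributions were used, best to worst:

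- uniform (0.2 each)
- symmetric (0.10, 0.20, 0.40, 0.20, 0.10)
- mild skew (0.40, 0.25, 0.15, 0.12, 0.08)
- skew (0.55, 0.25, 0.10, 0.06, 0.04)
- strong skew (0.75, 0.15, 0.05, 0.03, 0.02)

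The shift is proportional odds: for each cut, the HFNO odds of that category or better equal the control odds divided by OR. For example, with mild skew and OR 4, the best category has odds 0.40/0.60 = 0.667; 0.667/4 = 0.167, which is a probability of 0.14. The full HFNO distribution is then 0.14, 0.17, 0.18, 0.24, 0.26.

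Power over 3,000 simulated trials per setting, exact versions of both tests, range over the five distributions:

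| OR | Fisher 2×5 | Wilcoxon | Loss (points) |
|---|---|---|---|
| 2 | 11–13% | 16–22% | 5–10 |
| 3 | 24–28% | 37–48% | 12–19 |
| 4 | 38–44% | 55–66% | 17–22 |
| 6 | 61–67% | 80–86% | 19–21 |
| 10 | 86–89% | 96–98% | 8–10 |

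With no difference (OR 1), rejection rates were 4.1–5.0% for Fisher and 3.1–4.6% for exact Wilcoxon.

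A separate simulation (1,500 trials per setting; control 0.40, 0.25, 0.15, 0.15, 0.05 or uniform; tie-corrected asymptotic Wilcoxon) gave 43–44% against 64–67% at OR 4. The widest gap is 67 − 43 = 24 points, which is the upper end of the 12–24 range for ORs of 3–6.

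**4. Differences that are not a uniform shift.** For assumed polarised responses, power was 78% with Fisher and 7% with Wilcoxon. For a change confined to the top category it was 79% against 48%.

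**5. If categories were collapsed first.** A 2×2 Fisher test lost about 5 to 70 points against Wilcoxon, depending on cut and shift. With mild skew and the two central cuts at OR 3–4, the loss was 21–26 points.

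**The case against.** The strongest defence has four parts.

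- **Fisher's test is valid and omnibus.** It controls type I error and responds to any pattern of difference. A uniform shift is an assumption. Patients who could not tolerate a tight-fitting mask were excluded, and the HFNO flow was lowered for patients who did not tolerate it, so a mixed or polarised response cannot be ruled out. This stands: preferring an ordinal test means accepting less sensitivity to such patterns. For a better-or-worse question, the directional comparison is still the natural main one, and published category counts would show polarisation.
- **The 2×5 table is inferred.** The sentence also covers a proportion, and the scales may have been collapsed before testing. The ambiguity is real, and the table of losses applies only if they were not. Collapsing does not rescue the plan, because no cut-point is stated and it discards order too.
- **Small numbers dominate.** At OR 2 the chance of missing the difference is 87–89% with Fisher and 78–84% with Wilcoxon. A reader might infer that changing the test would make a null tolerability result trustworthy. It would not.
- **Changing a test after recruitment is itself a post hoc choice.** This also stands. The text is written in the past tense and already reports a change from non-inferiority to superiority after recruitment. A reader might take the change of test to be free of any drawback; it is not, and it has to be labelled.

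The absence of an effect size is partly a reporting matter: a Wilcoxon p value alone supplies none either, and nothing in the plan forbids showing the category proportions.

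**Conclusion.** The point holds in a conditional form. Both scales are ordered, and the stated test cannot use the order. At 20 per group, with all five categories tested and an assumed proportional-odds shift, the loss against Wilcoxon is about 5–10 points at OR 2, about 12–24 points at ORs of 3–6, and 8–10 points at OR 10. The ranking can reverse when the difference is not a shift.

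A reader might infer that the trial gives up a fixed amount, say 15–25 points. The documents do not support that: they contain no response distribution and no expected effect for either scale, and the loss falls below that range at OR 2 and OR 10. Nor do they support calling the tolerability analysis invalid. The matter is efficiency and interpretability of two secondary outcomes, and it does not touch the primary EtO₂ analysis.

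**What to change.** In the analysis paragraph, separate the two scales from the binary outcome:

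- Compare comfort and acceptability with an exact or tie-corrected Wilcoxon rank-sum test, or a proportional-odds model.
- Report the odds ratio, or the probability of a better rating, with a 95% CI. In the hypothetical example, the probability that a control patient gives the better rating, counting ties as half, is 1 − (325 − 210)/400 = 0.71.
- Show the full five-category counts by group for each scale.
- State whether categories were collapsed before the Fisher test and, if so, at which cut.
- Label the ordinal analysis post hoc and present the Fisher result beside it.
- Keep Fisher's test for the between-group comparison of the proportion reaching EtO₂ ≥ 90%.

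The cost is a few sentences and a re-run on data already collected. The drawbacks are lower sensitivity to differences that are not a shift, and one more post hoc analysis of secondary outcomes.
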